2. INTRODUCTION

2.1. Study Rationale

GlaxoSmithKline Biologicals SA (GSK) is developing a new RSV PreFusion protein 3 Older Adult (RSVPreF3 OA) investigational vaccine against respiratory syncytial virus (RSV)-associated (subtypes A and B) disease in adults \geq 60 years of age (YOA).

The RSVPreF3 OA investigational vaccine was administered intramuscularly for the first time to adults 60–80 YOA according to a 0, 2-month vaccination schedule in another clinical study (RSV OA=ADJ-002). The vaccine formulation and schedule to be used in the present study was selected based on safety and immunogenicity data from the RSV OA=ADJ-002 study.

The RSV OA=ADJ-004 is conducted to evaluate the safety, reactogenicity, immunogenicity profile and long-term persistence of the immune response up to 3 years following a single dose vaccination regimen of the RSVPreF3 OA investigational vaccine in adults \geq 60 YOA. Considering the uncertainty on the persistence of the immune response, this study is also designed to evaluate the immunogenicity, safety and reactogenicity of additional vaccine doses according to different revaccination schedules (annual revaccination or revaccination at a later stage).

The rationale for the study design is presented in Section 4.2.

2.2. Background

RSV is a ribonucleic acid virus of which 2 antigenically distinct subgroups exist, RSV-A and RSV-B [Borchers, 2013]. It is a highly contagious pathogen that causes respiratory tract infections in people of all ages. In temperate climates throughout the world, it predictably causes fall-winter epidemics. In (sub)tropical regions, viral activity is more endemic, and outbreaks are less temporally focused.

As the global population ages, the morbidity and mortality from respiratory infections appear to be steadily increasing in the older adult population [Lee, 2013; Binder, 2017]. Based on epidemiological data collected prospectively in 2008-2010 in 14 countries worldwide (including North America, Europe and East Asia), the average percentage of documented RSV infection in older adults with influenza-like illness is 7.4%, with values between 0% and 17.1% across countries [Falsey, 2014]. In 2015, an estimated 1.5 million episodes of RSV-related acute respiratory illness occurred in older adults in industrialized countries; approximately 14.5% of these episodes involved a hospital admission [Nam, 2019]. Further information on RSV incidence and disease burden can be found in the Investigator's Brochure (IB).

There is currently no vaccine or other prophylactic treatment available against RSV in older adults. Currently available treatment for RSV in this age group is generally supportive in nature, as detailed in the IB. Please refer to the current IB for information regarding pre-clinical and clinical studies of the RSVPreF3 OA investigational vaccine.

2.3. Benefit/Risk Assessment

2.3.1. Risk Assessment

Information about the known and expected benefits and risks and reasonably expected adverse events (AEs) of the RSVPreF3 OA investigational vaccine (potential syncope, hypersensitivity) or adjuvant system (potential immune-mediated diseases [pIMDs]) can be found in the IB and Development Safety Update Report.

All participants will remain under observation at the clinical center for at least 30 minutes after vaccination.

Intramuscular vaccination commonly precipitates a transient and self-limiting local inflammatory reaction. This may typically include pain at administration site, erythema, and swelling.

In addition to potential risks related to the vaccine, there may be risks related to the blood sampling planned in the study:

- Pain and bruising may occur at the site where blood is drawn; as a mitigation strategy, a topical analgesic may be applied to the site where blood will be taken.
- Syncope (fainting) can occur following or even before any blood draw as a psychogenic response to the needle insertion.

For details of study procedures, dose, and study design justification, refer to Sections 1.3 and 4.2.

2.3.2. Benefit Assessment

The participants may not directly benefit from vaccination with the RSVPreF3 OA investigational vaccine because vaccine efficacy has not been established yet. Hence it is not known whether the RSVPreF3 OA investigational vaccine is effective in protecting against RSV disease.

An indirect benefit is that the information obtained in this study will aid the development of an RSV vaccine, which is intended to prevent disease associated with RSV infection in older adults.

Another benefit for all study participants may include gaining information about their general health status through the medical evaluations/assessments associated with this study (i.e., physical examination).

2.3.3. Overall Benefit/Risk Conclusion

The RSVPreF3 OA investigational vaccine is in clinical development. Considering the measures taken to minimize the risk to participants in this study, the potential risks are justified by the potential benefits linked to the development of this vaccine.

3. OBJECTIVES AND ENDPOINTS

Table 6 Study objectives and endpoints

[figure not shown]
Objectives	Endpoints
Pr	imary
To evaluate the humoral immune response following a 1-dose primary schedule of RSVPreF3 OA investigational vaccine up to 12 months post-Dose 1.	Humoral immune response at pre-vaccination (Day 1), 30 days post-Dose 1 (Day 31), and at 6 and 12 months post-Dose 1 (Months 6 and 12), in a subset of participants: — Neutralizing antibody titers against RSV-A
	Neutralizing antibody titers against RSV-B.
Sec	ondary
To further evaluate the humoral immune response following a 1-dose primary schedule of RSVPreF3 OA investigational vaccine up to 12 months post-Dose 1.	Humoral immune response at pre-vaccination (Day 1), 30 days post-Dose 1 (Day 31), and at 6 and 12 months post-Dose 1 (Months 6 and 12), in a subset of participants: — RSVPreF3-specific Immunoglobulin G (IgG) antibody concentrations.
To evaluate the humoral immune response following 1 dose of the RSVPreF3 OA investigational vaccine and following revaccination doses, up to study end.	Humoral immune response at Months 18, 24, 30 and 36 post-Dose 1, and at 1 month after each revaccination dose (Months 13 and 25), in a subset of participants: - Neutralizing antibody titers against RSV-A and RSV-B - RSVPreF3-specific IgG antibody concentrations.
To evaluate the CMI response following 1 dose of the RSVPreF3 OA investigational vaccine and following revaccination doses up to study end.	CMI response at pre-vaccination (Day 1), 30 days post-Dose 1 (Day 31), at Months 6, 12, 18, 24, 30 and 36 post-Dose 1, and at 1 month after each revaccination dose (Months 13 and 25), in a subset of participants: — Frequency of RSVPreF3-specific CD4+ and/or CD8+ T cells expressing at least 2 activation markers including at least one cytokine among CD40L, 4-1BB, IL-2, TNF-α, IFN-γ, IL-13, IL-17.
To evaluate the safety and reactogenicity of each vaccination schedule of the RSVPreF3 OA investigational vaccine in all participants.	 Occurrence of each solicited administration site and systemic event during a 4-day follow-up period (i.e., on the day of vaccination and 3 subsequent days) after each vaccination. Occurrence of any unsolicited AE during a 30-day follow-up period (i.e., on the day of vaccination and 29 subsequent days) after each vaccination. Occurrence of all SAEs and pIMDs up to 6 months after each vaccination. Occurrence of fatal SAEs, related SAEs and related pIMDs from first vaccination (Day 1) up to study end (Month 36).
	rtiary
To further characterize immune responses to the RSVPreF3 OA investigational vaccine. CML = cell-mediated immunity. AE = adverse event. SAE	 Any further exploratory immunology in a subset of participants, such as, but not limited to: Antibodies against specific protein F epitopes. Potential new immunological markers for protection. Frequency of RSVPreF3-specific CD4+ and/or CD8+ T cells expressing one or any combination of immune marker(s).

CMI = cell-mediated immunity, AE = adverse event, SAE = serious adverse event, pIMD = potential immune-mediated disease.

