4. STUDY DESIGN

4.1. Overall Design

Figure 1 Study design overview (Amended: 01 April 2022)

ALS/SALS leading to withdrawar from study, ratar SALS

212496 (RSV OA=ADJ-004) Protocol Amendment 1 Final

N = number of participants; D = day; M = month; AE = adverse event; HI = humoral immunity; CMI = cell-mediated immunity; pIMD = potential immune-mediated disease; SAE = serious adverse event.

= blood sample for humoral immune responses (only applicable for ~ 345 participants of the RSV_annual group; and for all participants of the RSV_flexible revaccination and RSV_1dose groups)

= blood sample for CMI (only applicable for ~345 participants of the RSV_annual group, and for ~115 participants each from the RSV_flexible revaccination and RSV_1dose groups).

Note: For group RSV_annual: Revaccination Year 1 = Month 12; Revaccination Year 2 = Month 24; for group RSV_flexible revaccination: Revaccination Year 2 = Month 24. *Visit and follow-up of solicited events, unsolicited AEs, SAEs and pIMDs are only applicable for RSV_annual group.

**Visit and follow-up of solicited events, unsolicited AEs, SAEs and pIMDs are only applicable for RSV_annual and RSV_flexible revaccination groups.

^{***}For the RSV_annual group, the same ~345 participants will be part of both the HI and CMI subsets. The remaining ~645 participants will have no blood draws and will only be followed up for safety and reactogenicity.

^{****}For those participants in the RSV_annual group without blood sample collections, visits at Months 6, 18, 30 and 36 may be held through a contact. However, contact should be attempted only if site visit is not possible at Months 6, 18, 30 and 36.

- Type of study: Self-contained.
- **Experimental design**: Phase 3, randomized, open-label, multi-country study with 3 parallel groups (see Figure 1).
- **Duration of the study**: ~36 months for each participant.
- **Primary completion date**: Month 12.
- Control: None.
- **Blinding**: Open-label. Refer to Section 6.3.5 for details.
- Data collection: Standardized electronic Case Report Form (eCRF). Solicited events and unsolicited AEs will be collected using a participant Diary card (paper Diary card).
- **Safety monitoring**: The study will be conducted with oversight by the project Safety Review Team (SRT). Please refer to Section 8.2.2 for the description of review of safety data by the SRT.
- Study groups: refer to Figure 1 and Table 7 for an overview of the study groups.

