7.2. Participant discontinuation/withdrawal from the study

A participant is considered a 'withdrawal' from the study when no study procedure has occurred, no follow-up has been performed and no further information has been collected for this participant from the date of withdrawal/last contact.

From an analysis perspective, a 'withdrawal' from the study refers to any participant who did not return for the concluding visit foreseen in the protocol.

212496 (RSV OA=ADJ-004) Protocol Amendment 1 Final

Investigators will attempt to contact those participants who do not return for scheduled visits or follow-up.

All data and samples collected until the date of withdrawal/last contact of the participant will be used for the analysis.

The primary reason for study withdrawal will be documented in the eCRF based on the list below:

- AEs requiring expedited reporting to GSK (please refer to Section 10.3.10.1 for details)
- Unsolicited non-serious AE
- Solicited event
- Withdrawal by participant, not due to an AE*
- Migrated/moved from the study area
- Lost to follow-up
- Sponsor study termination
- Other (specify)

*If a participant is withdrawn from the study because he/she has withdrawn consent and provided the reason for its withdrawal, the investigator must document this reason in the eCRF.

Participants who are withdrawn from the study because of SAEs/AEs must be clearly distinguished from participants who are withdrawn for other reasons. Investigators will follow participants who are withdrawn from the study as result of an SAE/AE until the event is resolved (see Section 10.3.8.2).

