9.4.1.3. Reactogenicity/Safety

- For a given participant and the analysis of solicited events within 4 days post-vaccination, missing or non-evaluable measurements will not be replaced. Therefore, the analysis of solicited events will include only vaccinated participants with documented solicited safety data (i.e., paper diary completed).
- For analysis of unsolicited AEs, SAEs, pIMDs and concomitant medications, all vaccinated participants will be considered. Participants who did not report an event or concomitant medication will be considered as participants without the event or the concomitant medication, respectively.

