5.1.3. Reactogenicity/Safety

- For a given participant and the analysis of solicited events within 4 days postvaccination, missing or non-evaluable measurements will not be replaced. Therefore, the analysis of solicited events will include only vaccinated participants with documented solicited safety data (i.e., paper diary completed).
- For analysis of unsolicited AEs, serious adverse events (SAEs), potential immunemediated diseases (pIMDs) and concomitant medications, all vaccinated participants will be considered. Participants who did not report an event or concomitant medication will be considered as participants without the event or the concomitant medication, respectively.

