5.4.4. Safety analysis

Primary vaccination and revaccination dose:

The safety analysis will be performed on the ES. A descriptive analysis by group, for the 3 groups pooled up to Month 12, for the RSV_flexible revaccination and RSV_1dose groups pooled vs RSV_annual group for Month 13, Month 18 and Month 24, and by group from Month 25 up to study end, will present a summary of:

- The number and percentage of participants with at least one administration site event (solicited and unsolicited), with at least one systemic event (solicited and unsolicited) and with any AE during the 4-day or 30-day follow-up period will be tabulated with exact 95% CI after each dose. The same computations will be done for Grade 3 AEs, and for Grade 3 non-serious AEs and for AEs resulting in medically attended visit.
- The number and percentage of participants reporting each individual solicited administration site event (any grade, Grade 3 and resulting in medically attended visit) and solicited systemic event (any grade, Grade 3 and resulting in medically attended visit) during the 4-day follow-up period (i.e., on the day of vaccination and 3 subsequent days) will be tabulated for each group after each dose.
- For fever, the number and percentage of participants reporting fever by half degree (°C) cumulative increments during the 4-day follow-up period (i.e., on the day of vaccination and 3 subsequent days) will be tabulated for each group after each dose.
- The incidence of each solicited administration site event and solicited systemic event (any grade and grade 3) will be represented graphically after each dose.

- The number and percentage of participants with any unsolicited AEs during the 30day follow-up period (i.e., on the day of vaccination and 29 subsequent days) with its exact 95% CI will be tabulated for each dose by group and by Medical Dictionary for Regulatory Activities (MedDRA) Primary System Organ Class (SOC), High Level Term (HLT) and preferred term (PT). Similar tabulation will be done for Grade 3 unsolicited AEs, for any causally related unsolicited AEs, for Grade 3 causally related unsolicited AEs and for unsolicited AEs resulting in a medically attended visit. The verbatim reports of unsolicited AEs will be reviewed by a qualified person and the signs and symptoms will be coded according to the MedDRA Dictionary for Adverse Reaction Terminology. Every verbatim term will be matched with the appropriate Preferred Term.

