- The number and percentage of participants with at least one report of SAE classified by the MedDRA Primary SOC, HLT and PTs and reported from Dose 1 up to 6 months post-Dose 1 and from revaccination dose up to 6 months post-revaccination will be tabulated with exact 95% CI. The same tabulation will be presented for causally related SAEs and fatal SAEs,.
- The number and percentage of participants with at least one report of causally related SAEs classified by the MedDRA Primary SOC, HLT and PTs will be reported after each dose and from Day 1 up to study end with exact 95% CI. The same tabulation will be presented for fatal SAEs.
- All SAEs will also be described in detail in a tabular listing.
- All AEs/SAEs leading to study/intervention discontinuation from dose 1 up to study end will be tabulated.
- The number and percentage of participants with at least one report of pIMD classified by the MedDRA Primary SOC, HLT and PTs and reported from Dose 1 up to 6 months post-Dose 1 and from revaccination dose up to 6 months post-revaccination will be tabulated with exact 95% CI. The same tabulation will be presented for causally related pIMDs
- The number and percentage of participants with at least one causally related pIMD classified by the MedDRA Primary SOC, HLT and PTs will be reported after each dose and from Day 1 up to study end with exact 95% CI.
- All pIMDs will also be described in detail in a tabular listing.
- The analyses of unsolicited AEs will include SAEs (unless otherwise specified).

The analysis of safety will also be performed by age category (age at Dose $1: \ge 65$ YOA, ≥ 70 YOA, ≥ 80 YOA, 60-69 YOA and 70-79 YOA) and region (North America, Europe, Asia).

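### The Day 1 to Month 36 safety rows count early withdrawals as event-free, so the crude percentage understates 36-month risk; censored estimates should be added

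*Protocol*

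**What the plan says.** Protocol Section 3 (Table 6) sets a fixed window for this endpoint: "Occurrence of fatal SAEs, related SAEs and related pIMDs from first vaccination (Day 1) up to study end (Month 36"). Planned follow-up in Protocol 4.1 is about "36 months for each participant".

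The analysis is in SAP Amendment 3, Section 5.4.4. On the population: "The safety analysis will be performed on the ES". Causally related SAEs and related pIMDs are counts and percentages of participants that "will be reported after each dose and from Day 1 up to study end with exact 95% CI", and fatal SAEs get the same table. SAP 10.1.5.1 makes the interval Clopper-Pearson. Protocol 9.4.4.3 describes the same whole-study tabulations.

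The denominator rule is in Protocol 9.4.1.3: "For analysis of unsolicited AEs, SAEs, pIMDs and concomitant medications, all vaccinated participants will be considered". It continues: "Participants who did not report an event or concomitant medication will be considered as participants without the event or the concomitant medication, respectively". SAP 5.1.3 repeats it.

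Protocol 7.2 defines a withdrawal as someone for whom "no further information has been collected for this participant from the date of withdrawal/last contact". Protocol 10.3.8.1 stops collection of these events at discharge from the study. Protocol 9.2 says that withdrawals are not replaced.

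Neither document plans person-time, Kaplan-Meier or cumulative incidence for these events. The nearest provision is SAP 5.4.6. If more than 10% of participants miss revaccination or lack safety data after it, the safety analysis is repeated in those who attended every visit.

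**The concern.** A simple proportion with an exact binomial interval treats each participant as observed for the whole window. Here the window is three years in people aged 60 and over, and the rule for non-reporters turns an unobserved period into an event-free one. Events after withdrawal can be missed but never added, so in expectation the percentage lies at or below the true 36-month risk, and the interval moves down with it. That direction needs no model.

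These rows carry the long-term result for deaths and vaccine-related serious events by schedule. The study is descriptive, so the estimate and its interval are the result. The point concerns only the cumulative Day 1 to study end rows. It does not concern the tables after each dose or the denominators for a single revaccination window.

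**Working it through.** **The plan's own safety figures.** Protocol Table 23 uses P(at least one event) = 1 − (1 − p)^n. At p = 0.5%, 1 − 0.995^990 = 99.3% and 1 − 0.995^330 = 80.9%, as stated; all 30 cells reproduce. The table uses the full enrolled number with no loss. The immunogenicity tables do apply loss, at 20% a year: 1005 × 0.8 = 804 and 330 × 0.8² = 211.

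**Inputs.** From the documents: n = 990 (RSV_annual) and 330 (each other group), a 36-month window, and the counting rule above. Assumed, because the documents give neither: yearly loss d of 5%, 10% or 20%, and true 36-month risk R of 0.5%, 1% or 3%, with 5% as a stress case. The 20% is the Protocol 9.2 rate for non-evaluable participants. The glossary ties evaluability to the per-protocol analysis, so 20% serves only as an upper value for withdrawal.

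**Constant hazard.** Let λ = −ln(1 − R)/3 and μ = −ln(1 − d).

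- Average share of the 36 months observed = (1 − (1 − d)³) / (−3 ln(1 − d)) = 0.927, 0.857, 0.729 for d = 5%, 10%, 20%.
- Expected crude proportion = λ/(λ + μ) × (1 − exp(−3(λ + μ))). For R = 3% this is 2.78%, 2.57%, 2.19%.
- Relative shortfall: about 7%, 14%, 27%.

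Rounded to whole events with n = 990 and R = 3%:

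| Yearly loss | Events | Crude % | Exact 95% CI |
|---|---|---|---|
| 0% | 30 | 3.03 | 2.05–4.30 |
| 5% | 28 | 2.83 | 1.89–4.06 |
| 10% | 25 | 2.53 | 1.64–3.71 |
| 20% | 22 | 2.22 | 1.40–3.35 |

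**Coverage of the true risk by the Clopper-Pearson interval (exact binomial summation).**

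| n, true risk | 0% loss | 5% | 10% | 20% |
|---|---|---|---|---|
| 990, 3% | 95.9% | 94.0% | 88.7% | 67.3% |
| 990, 1% | 96.5% | 96.9% | 96.4% | 92.8% |
| 990, 0.5% | 98.0% | 98.2% | 98.1% | 97.2% |
| 330, 3% | 96.7% | 97.0% | 96.5% | 93.0% |
| 330, 1% | 98.1% | 98.7% | 99.2% | 99.7% |

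For n = 990 and R = 3%, the chance that the whole interval lies below the truth is 2.3%, 5.4%, 11.2% and 32.7% across the four loss rates. In the stress case (R = 5%), coverage at 5%, 10% and 20% loss is 92.1%, 82.5% and 46.8% for n = 990, and 96.4%, 94.4% and 85.4% for n = 330.

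**Events clustered after doses.**

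- RSV_1dose, events spread evenly over the first 6 months: ratio of crude to true = (1 − exp(−0.5μ))/(0.5μ) = 0.987 at d = 5% and 0.946 at d = 20%. The shortfall is about 1–5%.
- RSV_annual, equal risk immediately after each of three doses: ratio = (1 + (1 − d) + (1 − d)²)/3 = 0.951 and 0.813. The shortfall is about 5–19%.

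Equal loss therefore shrinks the two schedules by different amounts.

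**Whether SAP 5.4.6 repairs it.** It is conditional, and its trigger has no meaning for RSV_1dose, which has no revaccination. Requiring attendance at every visit removes anyone who died before Month 36, so the fatal-SAE figure there would be about zero. It also discards the time observed in people who withdrew.

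**The case against.** The strongest reply is that the practical effect may be small and that no decision hangs on it. The study is descriptive, no ratio between schedules is planned, and withdrawals are tabulated by group and reason, so a large imbalance in loss would be visible. Most of this stands and limits the point. It does not remove the bias, because a withdrawal count beside a crude percentage does not tell the reader what the 36-month risk is.

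A reader might also infer more than the documents support:

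- *That the exact CI is generally too low to trust.* The low coverage values depend on fairly common events in the 990-participant arm, or on the 20% ceiling. At 1% risk or less, or with n = 330, coverage is near or above nominal for 5–10% loss.
- *That 20% a year is the expected withdrawal.* Per-protocol elimination includes out-of-window samples and missing assay results (SAP Table 6), which do not end safety follow-up.
- *That equal risk will look different between schedules.* Loss of 10% in one arm and 20% in another would give 0.857/0.729 = 1.18 under constant hazard, but nothing in the documents indicates unequal withdrawal. With 25 against 7 events, sampling error alone is a factor of exp(1.96 × √(1/25 + 1/7)) ≈ 2.3 either way.
- *That these rows are the only long-term safety result.* SAP 5.4.4 also tabulates AEs/SAEs leading to discontinuation up to study end, and lists all SAEs and pIMDs.
- *That nothing at all is learned after withdrawal.* Protocol 7.2 follows people withdrawn for an AE or SAE until it resolves, and Protocol 8.3.1 requires notification of related SAEs that the investigator learns of after discharge. Neither route is active, complete follow-up for later events.

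**Conclusion.** The point holds for the cumulative Day 1 to study end rows for fatal SAEs, related SAEs and related pIMDs. A participant who withdraws without a prior event is counted as event-free to Month 36, so the crude percentage understates 36-month risk whenever there is withdrawal, and SAP 5.4.6 does not correct it. An event before withdrawal is still counted, and a death under observation is itself a fatal SAE.

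The direction follows from the counting rule. The size cannot be fixed from the documents. Under constant hazard and loss independent of risk it is about 7%, 14% or 27% in relative terms at 5%, 10% or 20% yearly loss, the last an upper value. Constant hazard is doubtful for vaccine-related events. If they cluster after doses, the range is about 1–5% in RSV_1dose and 5–19% in RSV_annual. Failure of the interval is a secondary matter, confined mainly to fairly common events in RSV_annual. No hypothesis or primary result is affected.

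**What to change.** In SAP 5.4.4, keep n, the crude percentage and the exact CI for these rows, and add by group:

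- (a) person-years from Dose 1 to the first of event, death, withdrawal/last contact or Month 36, with the rate and its exact Poisson 95% CI;
- (b) for fatal SAEs, the Kaplan-Meier 36-month risk with 95% CI;
- (c) for related SAEs and related pIMDs, the 36-month cumulative incidence by Aalen-Johansen, with death as a competing event and a 95% CI.

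State that (b) and (c) assume censoring independent of event risk, and base any statement about 36-month risk on them. The rate in (a) is not enough for that purpose: it becomes a 36-month risk only under constant hazard, and it averages over three dose windows in one arm and one in another.

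The cost is a SAP wording change and a few table columns. Dose, event and last-contact dates are already part of the planned data. The reported risk will be slightly less favourable. Conduct and sample size do not change.
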